## 2.2. Study Design

[figure not shown]
*This is a multicenter, 2-part, sequentially conducted, randomized, double-blind, double-dummy, placebo-controlled, parallel-group evaluation of DGAT2i + ACCi as summarized in Figure 1.*

**Figure 1. Overall Study Design**

*Determination of eligibility will occur via a sequential, 2-step process starting with Prequalification visit (PreQ). Participants identified to be eligible at PreQ will transition to the main study, starting with Screening (SCR) visit. The double-confirmation (at PreQ and SCR) will permit progression of only a selected subset of participants confirmed to meet Sponsor-defined presumed NASH criteria (along with other eligibility criteria) to the Run-In/Visit 2. At the Run-In/Visit 2, stabilization of concomitant medicines may occur, as needed/appropriate (refer to Section 6.5 of the protocol). All eligible participants must complete the Run-In/Visit 2, followed by Baseline/Visit 3. On Day 1/Visit 4, participants who meet the randomization criteria (refer to Section 5.3 of the protocol) will be assigned to receive 1 of pre-defined double-blind, double-dummy regimens (refer to Section 4.1.1 [for Part 1] and Section 4.1.2 [for Part 2] of the protocol) for a duration of up to 6 weeks, refer to Figure 2 [updated to reflect the PACL that removed Acuson Sequoia® assessments].*

**Figure 2. Study Design for Part 1 and Optional Part 2**

In Part 1, approximately 90 participants (18 per group) with Sponsor-defined presumed NASH will be randomly assigned to the study intervention to ensure approximately 75 evaluable participants (15 per group) offer evaluable data. In Part 2, a maximum of 4 active doses (plus placebo) will be evaluated in Part 2; furthermore, the total number of participants will not exceed 90 (with no more than approximately 27 participants per each active dose).

### **3. ENDPOINTS AND BASELINE VARIABLES: DEFINITIONS AND CONVENTIONS**

#### **3.1. Primary Endpoint(s)**

##### **3.1.1. Liver Fat Assessed Using MRI-PDFF at Week 6**

Percent change from baseline in liver fat content measured at Week 6 using MRI-PDFF constitutes the primary endpoint. The analysis will be performed using the natural-logarithmic transformation of relative change from baseline as described in [Section 5.2.4](#).

Baseline is defined as described in [Section 3.4](#).

**Note:** Relative Change from Baseline = Post-dose timepoint Value / Baseline Value

#### **3.2. Secondary Endpoint(s)**

##### **3.2.1. Fasting Serum Triglycerides Over Time**

Percent change from baseline in fasting serum triglycerides over time constitutes one of the secondary endpoints. The analysis will be performed using the natural-logarithmic transformation of relative change from baseline over time as described in [Section 5.2.5](#).

Baseline is defined as described in [Section 3.4](#).

##### **3.2.2. Safety and Tolerability**

The proportion of participants with treatment-emergent adverse events (TEAEs) and clinically significant, abnormal clinical laboratory tests, vital signs, and 12-lead ECGs constitute the other secondary endpoint.

Baseline is defined as described in [Section 3.4](#).

#### **3.3. Other Endpoint(s)**

##### **3.3.1. Liver Fat determined by Quantitative Ultrasound Using FibroScan®**

Liver fat, as obtained by controlled attenuation parameter (CAP®) measurement using FibroScan®, will be assessed at timepoints described in the Schedule of Activities of the protocol. The analysis will be performed using the natural-logarithmic transformation of relative change from baseline as described in [Section 5.2.4](#).

Baseline is defined as described in [Section 3.4](#).

**Note:** Relative Change from Baseline = Post-dose timepoint Value / Baseline Value

##### **3.3.2. Liver Stiffness Determined by Quantitative Ultrasound Using FibroScan®**

Liver stiffness, as obtained by vibration-controlled transient elastography (VCTE™) measurement using FibroScan® will be assessed at timepoints described in the Schedule of Activities of the protocol.

Baseline is defined as described in [Section 3.4](#).

### **3.3.3. Liver Function Tests Over Time**

Liver function tests include ALT, AST, ALKP, GGT, and Total Bilirubin. For all these laboratory parameters, baseline is defined as described in [Section 3.4](#).

#### **3.3.3.1. Alanine Aminotransferase (ALT)**

Alanine Aminotransferase (ALT) levels will be assessed at timepoints described in the Schedule of Activities of the protocol.

Percent change from baseline in ALT over time will be the endpoint of interest. The analysis will be performed using the natural-logarithmic transformation of relative change from baseline as described in [Section 5.2.5](#).

#### **3.3.3.2. Aspartate Aminotransferase (AST)**

Aspartate Aminotransferase (AST) levels will be assessed at timepoints described in the Schedule of Activities of the protocol.

Percent change from baseline in AST over time will be the endpoint of interest. The analysis will be performed using the natural-logarithmic transformation of relative change from baseline as described in [Section 5.2.5](#).

#### **3.3.3.3. Alkaline Phosphatase (ALKP)**

Alkaline Phosphatase (ALKP) levels will be assessed at timepoints described in the Schedule of Activities of the protocol.

Percent change from baseline in alkaline phosphatase over time will be the endpoint of interest. The analysis will be performed using the natural-logarithmic transformation of Relative change from baseline as described in [Section 5.2.5](#).

#### **3.3.3.4. Total Bilirubin (TBIL)**

Total Bilirubin (TBIL) levels will be assessed at timepoints described in the Schedule of Activities of the protocol.

Percent change from baseline in total bilirubin over time will be the endpoint of interest. The analysis will be performed using the natural-logarithmic transformation of relative change from baseline as described in [Section 5.2.5](#).

#### **3.3.3.5. Gamma Glutamyl Transferase (GGT)**

Gamma Glutamyl Transferase (GGT) levels will be assessed at timepoints described in the Schedule of Activities of the protocol.

Percent change from baseline in GGT over time will be the endpoint of interest. The analysis will be performed using the natural-logarithmic transformation of relative change from baseline as described in [Section 5.2.5](#).

### **3.3.4. Metabolic Parameters Over Time**

All of the following parameters, assessed following a fast of at least 8 hours (except HbA1C which is deemed evaluable even when assessed in a non-fasted state), will have baseline defined as described in [Section 3.4](#).

#### **3.3.4.1. Total Cholesterol**

Total Cholesterol levels will be assessed at timepoints described in the Schedule of Activities of the protocol.

Percent change from baseline in total cholesterol over time will be the endpoint of interest. The analysis will be performed using the natural-logarithmic transformation of relative change from baseline as described in [Section 5.2.5](#).

#### **3.3.4.2. Direct Low Density Lipoprotein (Direct LDL)**

Direct Low Density Lipoprotein (Direct LDL) levels will be assessed at timepoints described in the Schedule of Activities of the protocol.

Percent change from baseline in direct LDL over time will be the endpoint of interest. The analysis will be performed using the natural-logarithmic transformation of relative change from baseline as described in [Section 5.2.5](#).

#### **3.3.4.3. High Density Lipoprotein Cholesterol (HDL-C)**

High Density Lipoprotein cholesterol (HDL-C) levels will be assessed at timepoints described in the Schedule of Activities of the protocol.

Percent change from baseline in HDL-C over time will be the endpoint of interest. The analysis will be performed using the natural-logarithmic transformation of relative change from baseline as described in [Section 5.2.5](#).

#### **3.3.4.4. Direct Very Low Density Lipoprotein (Direct VLDL)**

Direct Very Low Density Lipoprotein (Direct VLDL) levels will be assessed at timepoints described in the Schedule of Activities of the protocol.

The analysis will be performed using the natural-logarithmic transformation of relative change from baseline as described in [Section 5.2.5](#).

#### **3.3.4.5. Apolipoproteins**

The apolipoproteins of interest are apolipoprotein A1 (ApoA1), apolipoprotein B Total (ApoBTotal), apolipoprotein B100 (ApoB100), apolipoprotein B48 (ApoB48), apolipoprotein C3 (ApoC3), and apolipoprotein E (ApoE) and their levels will be assessed at timepoints described in the Schedule of Activities of the protocol.

For each apolipoprotein described above, percent change from baseline over time will be the endpoint of interest. The analysis will be performed using the natural-logarithmic transformation of relative change from baseline as described in [Section 5.2.5](#).

#### **3.3.4.6. Derived non-High-Density Lipoprotein Cholesterol (Non-HDL-C)**

Non High-Density Lipoprotein cholesterol (Non-HDL-C) levels will be derived, as follows, at timepoints described in the Schedule of Activities of the protocol for *fasting TG, direct LDL-C, HDL-C, total cholesterol* -

Derived non-HDL-C = total cholesterol minus HDL-C

where all parameters are reported in mg/dL.

Percent change from baseline over time will be the endpoint of interest. The analysis will be performed using the natural-logarithmic transformation of relative change from baseline as described in [Section 5.2.5](#).

#### **3.3.4.7. Glycated Hemoglobin A1C (HbA1C)**

Glycated Hemoglobin A1C (HbA1C) levels will be assessed at timepoints described in the Schedule of Activities of the protocol.

The change from baseline in HbA1C over time will be the endpoint of interest and will be analyzed as described in [Section 5.2.5](#).

#### **3.3.4.8. Fasting Plasma Glucose (FPG)**

Fasting Plasma Glucose (FPG) levels will be assessed at timepoints described in the Schedule of Activities of the protocol.

The change from baseline in FPG over time will be the endpoint of interest. and will be analyzed as described in [Section 5.2.5](#).

#### **3.3.4.9. Fasting Plasma Insulin (FPI)**

Fasting Plasma Insulin (FPI) levels will be assessed at timepoints described in the Schedule of Activities of the protocol.

The change from baseline in FPI over time will be the endpoint of interest and will be analyzed as described in [Section 5.2.5](#).

#### **3.3.4.10. Homeostatic Model Assessment for Insulin Resistance (HOMA-IR)**

The change from baseline in HOMA-IR over time will be the endpoint of interest. The change from baseline in HOMA-IR over time will be the endpoint of interest and will be analyzed as described in [Section 5.2.5](#).

As described in the Schedule of Activities of the protocol, HOMA-IR values will be derived at each timepoint as follows:

$$\text{HOMA-IR} = (\text{Glucose}_{\text{Fasting Concentration}} \times \text{Insulin}_{\text{Fasting Concentration}}) / 405$$

where fasting plasma glucose concentrations is reported in mg/dL and fasting plasma insulin is reported in mU/L. As such, HOMA-IR is unit-less.

### 3.3.5. Biomarkers

Baseline for all the following endpoints is defined as described in [Section 3.4](#).

#### 3.3.5.1. Markers of Apoptotic Activity (CK18-M30 and CK18-M65)

Markers of apoptotic activity will be assessed at timepoints described in the Schedule of Activities of the protocol. These include the caspase-cleaved cytokeratin-18-M30 (ie CK18-M30) produced during apoptosis or the caspase-cleaved and intact cytokeratin-18-M65 (ie CK18-M65) usually released from cells undergoing necrosis.

The percent change from baseline in CK18-M30 and CK18-M65 over time will be the endpoints of interest. The analysis will be performed using the natural-logarithmic transformation of relative change from baseline as described in [Section 5.2.5](#).

#### 3.3.5.2. Markers of fibrinogenesis (ProC3 and ProC6)

Markers of collagen/fibrin formation will be assessed at timepoints described in the Schedule of Activities of the protocol. These include N-terminal pro-peptide of type III procollagen (ie ProC3) or C-terminal fragment of the  $\alpha 3$  chain of procollagen type VI (ie ProC6).

The percent change from baseline in ProC3 and ProC6 over time will be the endpoints of interest. The analysis will be performed using the natural-logarithmic transformation of relative change from baseline as described in [Section 5.2.5](#).

#### 3.3.5.3. Proprotein Convertase Subtilisin/Kexin Type 9 (PCSK9)

Proprotein convertase subtilisin/kexin type 9 (PCSK9) levels will be assessed at timepoints described in the Schedule of Activities of the protocol.

The percent change from baseline in PCSK9 over time will be the endpoints of interest. The analysis will be performed using the natural-logarithmic transformation of relative change from baseline as described in [Section 5.2.5](#).

#### 3.3.5.4. Adiponectin

Adiponectin levels will be assessed at timepoints described in the Schedule of Activities of the protocol.

The percent change from baseline in adiponectin over time will be the endpoints of interest. The analysis will be performed using the natural-logarithmic transformation of relative change from baseline as described in [Section 5.2.5](#).

### 3.3.5.5. High Sensitive C-Reactive Protein (hsCRP)

High Sensitive C-Reactive Protein (hsCRP) will be assessed at timepoints described in the Schedule of Activities of the protocol.

The percent change from baseline in hsCRP over time will be the endpoints of interest. The analysis will be performed using the natural-logarithmic transformation of relative change from baseline as described in [Section 5.2.5](#).

## 3.4. Baseline Variables

Baseline for all endpoints described in section 2, section 3, section 5 and section 6 is defined as the evaluable result closest **prior** to dosing on Day 1 0H (ie pre-dose).

In Particular, for each participant, for each of the following parameters, baseline will be defined as:

- Liver fat content, via MRI-PDFF, defined as the value of WLPDFF (see Appendix 2.2.1) obtained between Visit 3 and Visit 4 (ie, labeled as baseline)
- Liver fat assessment via CAP® using FibroScan® obtained between Visit 3 and Visit 4 (ie, labeled as baseline)
- Liver stiffness assessment via VCTE® using FibroScan® obtained between Visit 3 and Visit 4 (ie, labeled as baseline)
- Result closest prior to dosing on Day 1 [Visit 4] for the remaining pharmacodynamic endpoints **and all** safety-related continuous endpoints
  - As such would be results as reported on Day 1 [ Visit 4], and if these are not reported would be the results reported on Day -14 [Visit 3]
  - If results on Day 1 [Visit 4] and on Day -14 [Visit 3] are missing the baseline will be considered as missing.
- For Adverse events, refer to definition of treatment-emergent outlined in [Section 3.5.1](#).

Change from baseline (CBL), relative change from baseline (RCBL) and percent change from baseline (PBL) will be calculated as follows:

- CBL = Observed Value – Baseline Value
- RCBL = Observed Value / Baseline Value
- PBL =  $100 \times (\text{Observed Value} - \text{Baseline Value}) / \text{Baseline Value}$

## 3.5. Safety Endpoints

### 3.5.1. Adverse Events

Any adverse event included in the adverse CRF page will be considered as treatment emergent.

In fact, an adverse event will be considered ***treatment emergent*** (ie, TEAEs) relative to a given treatment if:

- event occurs for the first time during the effective duration of treatment and was not seen prior to 1st dose of double-blinded study medication on Day 1 [Visit 4], for example, during the interval between when participants offered informed consent for pre-qualification up to the day prior to 1st dose
- ***NOTE:*** Adverse events deemed non-treatment emergent observed during the interval between when participants offering informed consent for pre-qualification up to 1st dose on Day 1 (Visit 4) but resolved before 1st dose on Day 1).

The effective duration of treatment is determined by the lag time defined as the Pfizer Standard of 999 days post last dose of double-blinded study medication. Any ***treatment-emergent*** event occurring within the lag time, whether it occurs during a break in treatment or at the end of treatment, will be attributed to the assigned randomized regimen.

A 3-tier approach will be used to summarize TEAEs. Under this approach, TEAEs will be classified into 1 of 3 tiers. Different analyses will be performed for different tiers (See [Section 6.6.1](#)).

***Tier-1 events:*** These are pre-specified events of clinical importance (TMEs, DMEs, and CPTs) and are maintained in a program level list in CATEList.

***Tier-2 events:*** These are events that are not tier-1 but are “common”. A MedDRA preferred term (PT) is defined as a tier-2 event if there are at least 4 participants with at least one occurrence in any treatment group, per Pfizer Standard to distinguish Tier-2 events from Tier-3 events.

***Tier-3 events:*** These are events that do not meet criteria for either tier-1 nor tier-2 events

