#### **Study conduct and Baseline characteristics of Population Randomized:**

- Study conduct issues (e.g., enrollment status, currentness of the database, time between randomization and first treatment, eligibility violations)
- Participant evaluation groups
- Demographic and other baseline characteristics

**Safety Data:** The Committee will monitor certain specific safety-related laboratory parameters, vital sign parameters, and treatment-emergent adverse events (TEAEs) as well as serious adverse events (SAEs including death) listings in an unblinded manner for overall frequency of events. To do so, the listings which will be provided include:

- TEAEs (and SAEs) leading to temporary discontinuation of dosing;
- TEAEs (and SAEs) leading to permanent discontinuation and withdrawal;
- The listing of individual TEAEs and SAEs;
- All instances of hyperglycemia, or platelet reduction, or hypertriglyceridemia leading to permanent withdrawal;
- Listing of Treatment emergent adverse events (TEAEs) as defined in section 6.6 of this SAP;
- Listings of SAEs/deaths and narratives requested from the safety database (ie, ARGUS or similar)
- eGFR values and laboratory parameters outlined in Table 2 of this SAP represent the minimum list of parameters which will be listed and provided to the committee.
- This list may be expanded depending on team blinded review.

The Committee will receive the distribution of participants over time whose values cross the boundaries (ie Flag and Alert levels separately) for each of the parameters included in Table 2 of this SAP.

Percent change from baseline in fasting lipid parameters (ie triglycerides, total cholesterol, direct LDL-C, VLDL, HDL-C, and derived non-HDL-C), fasting apolipoproteins (ie ApoA1, ApoBtotal, ApoB100, ApoB48, ApoC3, and ApoE), liver function parameters (ie ALT, AST, Total Bilirubin, GGT, and Alkaline Phosphatase), eGFR, and will be provided for review.

Change from baseline in glycemic parameters (ie HbA1c, FPI and FPG) will be provided for review as well.

The following graphical representations will be provided:

- Box and whiskers plots of percent change from baseline for parameters in Table 2, eGFR, fasting lipid parameters (see list above), fasting apolipoproteins (see list above), and liver function test.
- Box and whiskers plots of changes from baseline for glycemic parameters (see list above):

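### SAP 3.5.1 gives two treatment-emergent AE rules without ranking them; they can disagree on worsened pre-Day 1 conditions and, depending on CRF routing, on placebo-period AEs (minor)

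*SAP*

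**What the plan says.** SAP 3.5.1 opens with a test of location on the CRF: "Any adverse event included in the adverse CRF page will be considered as treatment emergent". The next sentence, introduced as if it explained the first, sets a test of first occurrence. The bullet under it requires that the "event occurs for the first time during the effective duration of treatment and was not seen prior to" the first double-blind dose on Day 1. It illustrates the earlier period with an interval: "for example, during the interval between when participants offered informed consent for pre-qualification up to the day prior to" that dose. A NOTE then classes as non-treatment-emergent those AEs observed from pre-qualification consent up to the first "dose on Day 1 (Visit 4) but resolved before" that dose.

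The bullet and the NOTE do not mention worsening. Protocol 10.3.1 makes an increase in the frequency or intensity of a pre-existing condition an AE in its own right. Protocol 8.3.1.2 sends AEs that begin before study intervention to the Medical History page and later ones to the AE page.

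Two cross-references might have settled the order, but neither does. SAP 3.4 says "For Adverse events, refer to definition of treatment-emergent outlined in" Section 3.5.1, which only returns the reader to the two rules. SAP 7.1.1 promises the IRC a "Listing of Treatment emergent adverse events (TEAEs) as defined in section 6.6 of this SAP", and SAP 6.6 uses the term without defining it.

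**The concern.** The proportion of participants with TEAEs is a secondary endpoint (SAP 3.2.2). TEAE incidence and severity are the primary AE analyses (SAP 6.6.1), and TEAEs also feed the tiered risk differences and the IRC listings. With two unranked rules, two programmers working from the same data could report different counts.

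The worsening case carries more weight. It arises after randomization, so a drug effect on an existing condition could be left out of the count. Protocol 5.1 criterion 3 requires at least two of five metabolic criteria at entry, so pre-existing conditions will be common in this population.

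**Working it through.** The documents give no AE rates by period and no count of worsened conditions, so there is no plan figure to reproduce. The check applies each rule to each type of event.

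**Inputs**
- The two rules and the NOTE: SAP 3.5.1.
- Worsening is an AE: Protocol 10.3.1.
- CRF routing turns on the start of study intervention: Protocol 8.3.1.2.
- When study intervention starts. Protocol 6 lists matching placebo as study intervention, and 8.2.6 names the single-blind placebo from Visit 3. On the other side, Protocol 5.3 criterion 9 and 6.5 tie dosing to Day 1.

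**Comparison** (TE = treatment-emergent)

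| Event | AE-page rule | First-occurrence bullet |
|---|---|---|
| New onset after first double-blind dose | TE | TE |
| (a) Pre-Day 1 condition or AE worsens on double-blind drug, worsening on AE page; event read as the condition | TE | not TE |
| (a) Same; event read as the recorded worsening | TE | TE |
| (b) Placebo-period AE on AE page, no later worsening | TE | not TE (the NOTE agrees if it resolved) |
| Placebo-period AE on Medical History page | not TE | not TE |
| AE between consent and Visit 3, on Medical History page | not TE | not TE |

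The rules therefore disagree in (a) on one reading of the word event, and in (b) on one reading of the CRF routing. If the AE-page rule governs, (a) is counted and only (b) can be wrong, as an over-count. If the bullet governs, (b) is excluded and only (a) can be wrong, as an under-count.

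**Scale.** One reclassified participant changes an arm's incidence by 1/n:
- Part 1 arm, n = 18: 1/18 = 5.6 points.
- Part 2 active arm at the stated maximum of about 27: 1/27 = 3.7 points.
- A dose repeated in both parts and pooled, 18 + 27 = 45: 1/45 = 2.2 points.

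A non-Tier-1 term enters Tier 2 with "at least 4 participants with at least one occurrence in any treatment group". Four participants are 4/18 = 22.2%, 4/27 = 14.8% or 4/45 = 8.9% of those arms. As an illustration with assumed counts, suppose a term has 4/18 in one arm and no other group reaches 4. Reclassifying one of the four leaves 3/18 = 16.7%. The term drops to Tier 3 and its risk difference and interval are no longer shown, although it is still tabulated (SAP 6.2.2).

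**The case against.** The strongest reply to (a) is that the subject of the bullet is an adverse event and that Protocol 10.3.1 makes the exacerbation itself the AE. A stable condition is not an AE, so a recorded exacerbation that starts on double-blind drug is a first occurrence and both rules count it. This is a natural reading and narrows the point. It does not close it, because the SAP does not state that reading. It is also least comfortable for an AE that began between consent and Day 1 and later worsened, since that AE had itself been seen before the first dose. One could add that the bullet says if, not only if. That would make the AE-page rule decisive, which removes (a) but leaves (b) open.

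The reply to (b) is that the AE-page rule presupposes the routing in Protocol 8.3.1.2, and that the specific NOTE should override the general opening sentence for resolved events. Placebo-period events also precede randomization, so they are expected to balance across arms. The balance argument stands. The override is plausible but not stated, and it does not reach events still ongoing at Day 1.

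A reader might infer two further gaps that the text does not support:
- *Events ongoing at Day 1 without worsening.* The NOTE covers only resolved events, but an ongoing event was seen before the first dose and so already fails the bullet.
- *Day 1 onsets before dosing.* The interval ending the day before the first dose is only an example. The operative test is whether the event was seen before that dose, so these onsets also fail the bullet.

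Nor do the documents support reading this as a threat to the trial's conclusions. No formal hypothesis tests are planned, and SAP 6.6.1 limits AE p-values and intervals to screening. The laboratory flag and alert counts and the triglyceride and platelet analyses do not use TEAE status.

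**Conclusion.** The point holds, as a minor one. SAP 3.5.1 states two different tests for one secondary endpoint and does not rank them. Followed literally, the bullet can drop a worsening on double-blind drug, or the AE-page rule can count an event from the placebo period, but not both under the same rule.

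The conclusion rests on two conditions. Case (a) needs the event to be read as the condition or the earlier AE rather than the recorded worsening. Case (b) needs Protocol 8.3.1.2 to treat Visit 3 placebo as study intervention; if it means the Day 1 dose, (b) does not arise. The number affected cannot be estimated from the documents. What can be stated is the unit effect of 5.6 points per participant in an 18-participant arm.

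**What to change.** Replace the opening sentence and the bullet of SAP 3.5.1 with one governing rule:
- A TEAE is an AE with onset on or after the first double-blind dose, including a worsening in intensity or frequency after that dose of a condition or event present before it.
- An AE that starts before that dose and does not later worsen is not treatment-emergent.
- Location on the AE page does not by itself determine status.

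As a minor edit, point SAP 7.1.1 to 3.5.1 for the definition. A separate listing of AEs from Visit 3 to the first double-blind dose is optional and depends on the CRF holding onset dates for them.

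The cost is SAP wording and one derivation, plus the listing if wanted. The rule relies on sites recording a worsening as its own AE with an onset date. It is best settled before unblinding, so that the choice cannot depend on the counts.
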